6.4 Lenalidomide (RevlimidTM)

6.4.1 Lenalidomide Administration and Schedule

Lenalidomide will be given orally. The starting dose is 25 mg days 1-21 of a 28 day cycle. If a dose is missed or vomited up, the dose will not be made up. Lenalidomide doses may be consumed at any time during a dosing day without being considered 'delayed' or 'missed.'

In the event of a dose hold due to toxicity, the patient's treatment will be considered delayed and not missed.

Beginning on day 1 of cycle #2 and on day 1 of every cycle thereafter, while all conditions below have been met, patients will be evaluated for lenalidomide dose reduction.

For patients that:

- Never had a lenalidomide dose reduction due to a toxicity that was probable or definitely related to lenalidomide.
- Maintained platelet count $\geq 50,000$ at all times in the previous cycle
- Minimum ANC $\geq 1,000$ at all times in the previous cycle
- No clinically significant grade 2 or greater non-hematologic toxicities in the previous cycle

If all conditions are met, no dose reduction will occur. If any of the above conditions is not met, the patient's dose for lenalidomide will be reduced by 5 mg.

Per lenalidomide prescribing information, the starting dose of lenalidomide for patients enrolled with creatinine clearance (Clcr) < 50 mL/min will be 10mg days 1-21 of a 28 day cycle.

Dose reductions are not permanent. Lenalidomide may be increased again per treating physician discretion. In the event a patient is dose reduced to 0mg, patient may continue on study, and may still receive Nivolumab as scheduled.

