6.5.1 Table 6.5.1 Adverse events and Dose Adjustment of drugs

Neutropenia	Grade 3 or greater on day 1 of cycle: delay and monitor CBC weekly; if resolves to \leq grade 2 within 4 weeks, resume lenalidomide with 5mg dose reduction. If grade 3 or greater during a cycle, hold lenalidomide for the remainder of the cycle. Resume with 5mg dose reduction for subsequent cycles. G-CSF or GM-CSF are not to be used to avoid dose reductions but can be used for treatment of febrile neutropenia
Febrile Neutropenia	Hold lenalidomide for the remainder of the cycle. Consider G-CSF administration until there is adequate count recovery $ANC \geq 1000/\mu L$ + absence of fever. If neutropenia resolves \leq grade 2, resume lenalidomide at 5 mg dose reduction for subsequent cycles.
Thrombocytopenia	If grade 3 or greater, hold lenalidomide for the remainder of the cycle and until platelets $\geq 50,000/\mu L$. Then resume lenalidomide at 5 mg dose reduction for subsequent cycles.
Anemia	For grade 3 or greater, hold lenalidomide for the remainder of the cycle and until hemoglobin recovers to \leq grade 2.
Fatigue (asthenia, malaise) Lenalidomide or dexamethasone	For intolerable grade 2 or grade 3-4, hold the protocol therapy thought to be probable or definitely related to the reaction until resolves to \leq grade 1, then resume protocol therapy with dose reduction of implicated protocol therapy by one dose level (5 mg for lenalidomide and/or 50% for dexamethasone).
Rash Lenalidomide	If grade 3 or greater, hold lenalidomide until resolves to \leq grade 2, then resume protocol therapy. In the instance of intolerable recurrent rash, stop implicated drug but may continue on study.
Renal insufficiency	For patients with calculated or measured GFR $<30\text{ml/min}$, lenalidomide should be held until creatinine returns to baseline. If the calculated or measured GFR falls under 50 ml/min, the dose of lenalidomide will be reduced to 10mg if the patient began therapy with 25mg dosage.
Venous Thromboembolism	All protocol should be held until the patient is adequately anti-coagulated. Patients with recurrent thrombosis despite adequate anti-coagulation should be removed from protocol therapy.

Suspected Pregnancy	Protocol therapy should be held until pregnancy is ruled out. Discontinue all protocol therapy if pregnancy is positive

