6.7 Requirements at the beginning of each cycle

A new course of treatment may begin on the scheduled Day 1 of a new cycle if:

- The ANC is $\geq 1,000/\mu\text{L}$;
- The platelet count is $\geq 50,000/\mu\text{L}$;
- Any lenalidomide-related allergic reaction/hypersensitivity or sinus bradycardia/ other cardiac arrhythmia adverse event that may have occurred has resolved to \leq grade 1 severity;
- Any other lenalidomide-related adverse event that may have occurred has resolved to \leq grade 2 severity.

If these conditions are not met on Day 1 of a new cycle, the subject will be evaluated weekly and a new cycle of therapy will not be initiated until the toxicity has resolved as described above. Patients unable to initiate a new cycle of therapy within 4 weeks due to treatment related toxicity will be removed from study.

- If lenalidomide dosing was held during the previous cycle and was restarted with a one-level dose reduction without requiring an interruption for the remainder of the cycle, then that reduced dose level will be initiated on Day 1 of the new cycle.
- If lenalidomide dosing was omitted for the remainder of the previous cycle or if the new cycle is delayed due to lenalidomide related toxicity newly encountered on the scheduled Day 1, then the new cycle will be started with a one-level dose reduction of lenalidomide.

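### After a hold for lenalidomide-related Grade 3+ anemia, Section 6.7 cuts the next lenalidomide dose one level, Section 6.4.1 read literally does not, and the anemia row of Table 6.5.1 is silent

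*Combined protocol and SAP*

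**What the plan says.** Three places in the combined protocol and SAP govern the lenalidomide dose after an anemia hold.

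- **Table 6.5.1, anemia row.** For Grade 3 or greater, sites must "hold lenalidomide for the remainder of the cycle and until hemoglobin recovers to" Grade 2 or less. The row stops there. The neutropenia, febrile neutropenia and thrombocytopenia rows each add a 5 mg reduction on restart.
- **Section 6.7, last bullet.** There are two triggers: doses left out to the end of the last cycle, and a hold-up in starting the new one. In either case "then the new cycle will be started with a one-level dose reduction of lenalidomide". The relatedness wording, "due to lenalidomide related toxicity newly encountered on the scheduled Day 1", comes directly after the second trigger. The section does not size a level; the fatigue row of Table 6.5.1 sets it at 5 mg for lenalidomide.
- **Section 6.4.1.** From cycle 2, day 1 of each cycle carries four tests: no earlier reduction for probably or definitely lenalidomide-related toxicity, platelets at least 50,000 and ANC at least 1,000 throughout the previous cycle, and no clinically significant Grade 2+ non-hematologic toxicity in it. "If all conditions are met, no dose reduction will occur"; otherwise the "dose for lenalidomide will be reduced by 5 mg".

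Section 6.4.1 also sets a lower start for renal impairment ("the starting dose of lenalidomide for patients enrolled with creatinine clearance (Clcr) < 50 mL/min will be 10mg") and lets the physician raise a reduced dose again. Section 5.2 lets a patient with a lenalidomide-related hematologic dose-limiting toxicity in cycle 1 continue with a standard-of-care reduction. Grade 4 anemia not explained by the disease is the only anemia on that list.

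**The concern.** Sections 6.4.1 and 6.7 are both written as mandatory and both act on day 1 of the next cycle. The anemia row, where a site would look first, does not choose between them, and no sentence ranks them. Section 6.4.2 has a heading about dose levels but lists none and sets no precedence.

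The trial has subsites (Section 4), so two sites that each follow the text could give different doses after the same event, before the response assessment at the end of cycle 4. Under 6.4.1 a patient goes back to the full dose after a related Grade 3 toxicity. Under 6.7 the dose of an anti-myeloma drug falls, by half for a patient who started at 10 mg.

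**Working it through.** The plan gives no figure to reproduce on this point. The check traces one patient through the rules and then sizes the difference.

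**Patient.** Lenalidomide-related Grade 3 anemia during a cycle; platelets and ANC above the thresholds throughout; no clinically significant Grade 2+ non-hematologic toxicity; no earlier lenalidomide-related reduction.

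**Trace.**

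| Rule | Applied to this patient | Next-cycle dose, 25 mg start | Next-cycle dose, 10 mg start |
|---|---|---|---|
| Table 6.5.1, anemia | Hold to end of cycle and until recovery | not stated | not stated |
| 6.7, last bullet | Dosing was omitted to the end of the cycle: one level down | 20 mg | 5 mg |
| 6.4.1 | All four tests passed: no reduction | 25 mg | 10 mg |

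Each qualifier matters. With low platelets, low ANC, clinically significant Grade 2 fatigue or an earlier related reduction, 6.4.1 also orders a 5 mg cut and the two rules agree. For a cycle-1 Grade 4 dose-limiting anemia, 5.2 sides with 6.7. What stays open is Grade 3 in any cycle and Grade 4 after cycle 1.

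**Next cycle, 21 doses.**

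- 25 mg start: 21 × 20 = 420 mg against 21 × 25 = 525 mg; 105/525 = 20% less under 6.7.
- 10 mg start: 21 × 5 = 105 mg against 21 × 10 = 210 mg; 105/210 = 50% less under 6.7.

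**Cycles 1 to 4.** Assumptions: hold from day 15 of cycle 1 (a scheduled blood count, Section 6.9.6), so 14 doses are taken in that cycle; recovery by the next day 1; no other event; no re-escalation. With starting dose d, the plan is 84d and 63 doses remain after cycle 1.

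- Planned: 84 × 25 = 2,100 mg, or 84 × 10 = 840 mg.
- No cut (6.4.1): 14d + 63d = 1,925 mg or 770 mg, 92% of plan in both cases.
- One 5 mg step kept (6.7): 14d + 63(d − 5) = 350 + 1,260 = 1,610 mg (77%), or 140 + 315 = 455 mg (54%).

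**Patients affected.** The document gives no anemia rate for lenalidomide or for the combination. Section 1.4.2 reports drug-related Grade 3+ anemia in 3 of 81 patients on nivolumab alone: 18 × 3/81 = 0.7. An assumed upper rate of 15% gives 18 × 0.15 = 2.7. Both figures count all such anemia, before the qualifiers above are applied.

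**Related mismatch.** Grade 3 neutropenia first found on day 1 also passes 6.4.1, whose count tests look back at the previous cycle, while its own row and 6.7 order a cut. Lenalidomide-related Grade 3 anemia first found on day 1 behaves the same way under 6.7.

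**The case against.** The strongest reply is that the document already supplies the dose. Section 6.7 addresses exactly this event, so the anemia row need not repeat it. Section 6.4.2 bases modifications on toxicity during a cycle or new on its first day, and 5.2 points the same way for cycle-1 Grade 4 anemia. The day-1 neutropenia case shows that 6.4.1 cannot have been meant to bar every other reduction, and its lead-in is loosely drafted. On this view 6.4.1 is a routine screen that works alongside the toxicity rules.

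Most of this stands as evidence of intent, and it is why the point is minor. It does not remove the contradiction. The sentence in 6.4.1 is unconditional once its tests are passed, no precedence is stated, 5.2 does not reach Grade 3 or later cycles, and the anemia row differs from the other three blood-count rows. Discretion to raise the dose later does not say which dose starts the cycle.

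A reader might also infer a ratchet. The first test in 6.4.1 is "Never had a lenalidomide dose reduction due to a toxicity that was probable or definitely related to lenalidomide". After a 6.7 cut for probably or definitely related anemia it can never be passed again, so a literal reading takes off 5 mg at every later cycle: 25, 20, 15, 10 mg (350 + 420 + 315 + 210 = 1,295 mg, 62% of plan), or 10, 5, 0, 0 mg (140 + 105 = 245 mg, 29%). The document does not support this as the intended dosing. Section 6.4.1 says reductions are not permanent, the preceding bullet of 6.7 carries a reduced level forward unchanged, and the figures also assume no re-escalation. They carry no weight in the conclusion; the wording is still worth repairing.

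**Conclusion.** The inconsistency is real but narrow. It needs a hold to the end of the cycle for lenalidomide-related Grade 3+ anemia as the sole trigger, no earlier lenalidomide-related reduction, and an event that is not a cycle-1 Grade 4 dose-limiting toxicity. In that case the next dose differs by 5 mg a day, which is 20% of a 25 mg dose or 50% of a 10 mg dose. Section 6.7 is probably the rule meant.

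Three wider inferences are not supported:

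- **An effect on response rate.** None is claimed. Few patients are likely to be affected, and the 18-patient design and its decision rules do not change. The 0.7 to 2.7 range rests on a nivolumab-only rate in mixed tumors and an assumed upper rate.
- **A conflict for disease-related anemia.** The relatedness phrase in 6.7 may qualify both of its clauses, so none is claimed there.
- **A problem confined to anemia.** Neutropenia first found on day 1 shows the same mismatch.

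This is an internal inconsistency of minor severity. It is worth correcting because the literal reading of 6.4.1 restarts the full dose after a related Grade 3 toxicity and the repair costs almost nothing.

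**What to change.** 1. **Anemia row, Table 6.5.1.** Keep the hold and add: *If the anemia is lenalidomide-related, restart 5 mg lower, as in Section 6.7.* The degree of relatedness required is a clinical choice for the sponsor. Section 6.4.1 and the fatigue row use probable or definite; a possible threshold would mandate more cuts.
2. **Section 6.4.1, new condition.** *Lenalidomide-related toxicity neither stopped dosing for the rest of the last cycle nor delayed this one.* Add that one event gives one 5 mg step in total across 6.4.1, Table 6.5.1 and 6.7, with the renal insufficiency row keeping its own dose. This also covers neutropenia first found on day 1.
3. **Section 6.4.1, first condition.** Replace it, so that a past reduction alone does not trigger another. One option: *No probably or definitely lenalidomide-related toxicity calls for a reduction that has not already been made.* Adding a disclaimer while leaving the present condition in place would only create a new contradiction.
4. **Section 6.7, last bullet.** State in the first clause that the omission was because of lenalidomide-related toxicity, so that disease-related anemia does not lead to a cut.

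The cost is one sentence in the table, one added condition, one replaced condition and one sentence in 6.4.1, and one phrase in 6.7. No tests are added, and sample size and analysis are unchanged.

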		
In addition to the criteria for permanent discontinuation of Nivolumab based on CTC grade/severity, permanently discontinue Nivolumab for the following:
 
 • Recurrence of a previously experienced Grade 3 treatment-related AE following resumption of dosing 	
alternative etiology (e.g. disease progression, concomitant medications, infections, etc)
 
 • In the absence of a clear alternative etiology, all events should be considered potentially immune related • Symptomatic and topical therapy should be considered for any low grade events (Grade 1 or 2, unless otherwise specified)
Grade 1		No dose modification	
Grade 2		
Hold Nivolumab dose until grade 2 resolution to grade 1
 
 • If toxicity worsens then treat as Grade 3 or Grade 4 • If toxicity improves to baseline then resume treatment as seen best by treating physician • Nivolumab can be resumed once event stabilizes to grade 1 and 5-7 days have passed after completion of steroid taper. 
Subjects with endocrinopathies who may require prolonged or continued steroid replacement can be retreated with Nivolumab on the following conditions: 1) the event stabilizes and is controlled, 2) the subject is clinically stable as per investigator or treating physician's clinical judgement, and 3) doses of prednisone are at less than or equal to 10 mg/day or equivalent
	
 • For persistent (greater than 3-5 days) low grade (Grade 2) or severe (Grade \geq 3) events promptly start prednisone PO 1-2 mg/kg/day or IV equivalent • If symptoms recur or worsen during corticosteroid tapering (28 days), increase the corticosteroid dose (e.g. up to 2-4 mg/kg/day or IV equivalent) until stabilization or improvement of symptoms, then resume corticosteroid tapering at a slower rate ($>$ 28 days of taper) • More potent immunosuppressives such as TNF inhibitors should be considered for events not responding to systemic steroids • Discontinuation of Nivolumab is not mandated for Grade 3/4 inflammatory reactions attributed to local tumor response (e.g. inflammatory reaction at sides of plasmacytomas). Continuation of study drug in this situation should be based upon a benefit/risk analysis for that subject
Grade 3		Depending on the individual toxicity, may permanently discontinue Nivolumab	
Grade 4		Permanently discontinue Nivolumab	

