	Grade 2	
Hold Nivolumab until Grade 2 resolution to \leq Grade 1
 
 • If toxicity worsens then treat as Grade 3 or 4 • If improves to baseline then treat at next scheduled treatment date • Nivolumab can be resumed once event stabilizes to grade 1 and 5-7 days have passed after completion of steroid taper. 	
For Grade 2 AST or ALT and/or total bilirubin elevation
 
 • Regular and frequent checking of LFTs (every 1-2 days) until elevations of these are improving or resolved • If no resolution to \leq grade 1 in 1-2 days, discuss with study physician • If event is persistent ($>$ 3-5 days) or worsens, promptly start prednisone 1-2 mg/kg/day or IV equivalent • If still no improvement within 3-5 days despite 1-2 mg/kg/day of prednisone or equivalent, consider additional workup and prompt treatment with IV methylprednisolone 2-4 mg/kg/day started • If still no improvement within 3-5 days despite 2-4 mg/kg/day methylprednisolone, promptly start other immunosuppressives (mycophenolate mofetil)

			
 Once improving, gradually taper steroids over \geq 28 days and consider prophylactic antibiotics, antifungals, and anti-PCP treatment
	Grade 3	For elevations in transaminases \leq 8 x ULN, or elevations in bilirubin \leq 5 x ULN: 
 Hold Nivolumab until resolution to \leq grade 1 or baseline Resume Nivolumab if elevations downgrade to \leq grade 1 or baseline within 14 days For elevations in transaminases $>$ 8 x ULN or elevations in bilirubin $>$ 5 x ULN, discontinue Nivolumab 	For Grade 3 or 4 AST or ALT and/or total bilirubin elevation: 
 Promptly initiate empiric IV methylprednisolone at 1-4 mg/kg/day or equivalent If still no improvement within 3-5 days despite 1-4 mg/kg/day methylprednisolone IV or equivalent promptly start immunosuppressive treatment (mycophenolate mofetil) Hepatology consult, abdominal workup, and imaging as appropriate Once improving, gradually taper steroids over \geq 28 days and consider prophylactic antibiotics, antifungals, and anti-PCP treatment
	Grade 4	Permanently discontinue Nivolumab	

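### The two Grade 3 hepatitis instructions in Table 6.5.2 overlap when both liver markers are raised and only one exceeds its limit, so a patient who recovers within 14 days is directed both to resume and to discontinue nivolumab

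*Combined protocol and SAP*

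**What the plan says.** Section 6.5.2, Table 6.5.2, Hepatitis, Grade 3, dose-modification column, has two branches.

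- **Branch 1 (hold, conditional resumption).** The condition is transaminases at or below "8 x ULN, or elevations in bilirubin" at or below 5 x ULN. The first action is "Hold Nivolumab until resolution to" Grade 1 or lower, or baseline. The second is "Resume Nivolumab if elevations downgrade to" that same level within 14 days.
- **Branch 2 (discontinuation).** The condition is transaminases above 8 x ULN or bilirubin above "5 x ULN, discontinue Nivolumab".

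The toxicity-management column of the same row covers "AST or ALT and/or total bilirubin elevation", so it provides for the two markers rising together as well as singly.

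The general entry for Grade 3 immune-related events at the start of Table 6.5.2 reads "Depending on the individual toxicity, may permanently discontinue Nivolumab". It is permissive and sends the reader back to the row for the specific toxicity.

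**The concern.** The two branches look like a split of Grade 3 hepatitis into a milder part and a more severe part. For a true split, one condition must be the negation of the other. The negation of a statement joined by *or* is a statement joined by *and*, so two conditions both joined by *or* must overlap somewhere. In the overlap the row gives two instructions and no order of precedence.

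What is at stake is re-exposure to nivolumab after Grade 3 liver toxicity. The trial has more than one site, and Section 16.2 requires it to be conducted as the protocol describes. For some patients, two sites could act in opposite ways on the same laboratory values and each cite the table.

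**Working it through.** This is a check of logic. The plan states no figure on this point, so there is none to reproduce.

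**Inputs.** All come from the Grade 3 hepatitis row of Table 6.5.2. Let T be transaminases and B bilirubin, each as a multiple of ULN, for an event graded 3.

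- H (hold, conditional resumption) = (T ≤ 8) or (B ≤ 5)
- D (discontinue) = (T > 8) or (B > 5)

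**Step 1. Literal reading.** The negation of H is (T > 8) and (B > 5). D is wider than that, so H and D hold together whenever exactly one marker exceeds its limit: 2 of the 4 cells, the discordant ones.

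**Step 2. Reading that gives weight to the word *elevations*.** The row speaks of elevations in each marker, so a normal marker arguably cannot meet the Branch 1 condition. Adding a normal level for each marker gives nine cells:

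| | B normal | B raised, ≤ 5 | B > 5 |
|---|---|---|---|
| T normal | neither | H | D |
| T raised, ≤ 8 | H | H | **H and D** |
| T > 8 | D | **H and D** | D |

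The overlap shrinks but remains. Two cells still meet both branches: those with both markers raised and only one above its limit. A patient with one marker above its limit and the other normal meets only D.

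**Step 3. When the actions are incompatible.** Holding a drug does not conflict with discontinuing it; resuming it does. Branch 1 directs resumption only if values reach Grade 1 or baseline within 14 days. The actions therefore diverge when three conditions hold together:

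1. both markers are raised;
2. exactly one exceeds its limit;
3. values recover to Grade 1 or baseline within 14 days.

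**Step 4. Example.** Take T = 12 and B = 2, recovering to Grade 1 on day 10. B ≤ 5 puts the patient in Branch 1, and recovery within 14 days means resume. T > 8 puts the same patient in Branch 2, which means discontinue.

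**Step 5. Is precedence stated elsewhere?** The general Grade 3 entry is permissive and sets no order. The Grade 4 hepatitis entry directs permanent discontinuation but does not apply to a Grade 3 event. No other section ranks the two branches.

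**Step 6. Likely size.** The drug-related adverse event table in Section 1.4.2 (81 patients on nivolumab alone) lists 2 hepatic events (ALT or AST increase) of any grade and 0 of Grade 3 or higher. The exact one-sided 95% upper bound for 0 of 81 is 1 − 0.05^(1/81) = 0.036. Applied to 18 patients it gives 18 × 0.036 ≈ 0.65 patients with any such event, before requiring discordant markers and recovery in 14 days. This assumes that single-agent experience carries over to the combination with lenalidomide, which the documents do not establish.

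**The case against.** The strongest reply is that the row has a workable ordinary reading. The first *or* lists whichever abnormality made the event Grade 3, and the second branch then takes out anyone with either marker above its limit. Many clinicians would probably read it so. That is plausible, but it is an inference: neither the row nor any other section says that Branch 2 overrides Branch 1.

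A second reply is that sites would not be acting unobserved:

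- the row calls for a hepatology consult;
- a Grade 3 treatment-related event that recurs after resumption requires permanent discontinuation (Table 6.5.2);
- potential drug-induced liver injury is a serious adverse event (Section 10.2), reportable within 24 hours (Section 10.3);
- three related immune-mediated events of Grade 3 or higher suspend the study (Section 5.3.1);
- cross-site calls are held at least monthly (Section 10.6).

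These reduce the chance that divergent handling goes unnoticed. None of them tells a site which branch to follow.

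A third reply is that the overlap is narrow. This stands. A reader might infer that every patient with exactly one marker above its limit receives contradictory orders, but on the reading of *elevations* in Step 2 a patient whose other marker is normal receives only the discontinue instruction. Nor does a count of two logical cells say how many patients fall in them. Patients with both markers raised cannot be dismissed as hypothetical, however: the management column provides for them, the drug-induced liver injury definition in Section 10.2 requires both markers to be raised, and Section 3.1 admits patients with AST or ALT up to 2 x ULN.

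**Conclusion.** Wrong as written, and minor. The Grade 3 hepatitis row contradicts itself for patients with both markers raised, exactly one above its limit, and recovery to Grade 1 or baseline within 14 days. For them it directs both resumption and discontinuation of nivolumab, with no rule of precedence anywhere in the protocol. This rests only on the wording of the row and holds on both the literal reading and the narrower one.

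The number of patients affected cannot be derived from the documents. It is likely to be small, given 0 of 81 in the protocol's own single-agent table, with the caveat about the combination.

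Two stronger conclusions should not be drawn. A reader might infer that nivolumab exposure or discontinuation rates would depend materially on who interprets the table; no figure in the documents supports that, and neither rate is a listed endpoint. A reader might also infer harm to the primary analysis. The response-rate design in Section 7.1.1 (18 patients, with its cut-offs) does not use this rule, and no effect on it has been shown.

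**What to change.** Reconcile the two branches so that every combination of transaminase and bilirubin values in a Grade 3 event leads to exactly one instruction. This can be done by making the two conditions complementary or by adding a sentence that says which branch prevails. Which instruction the discordant patients should receive is a clinical choice for the investigators, and this review takes no position on it.

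One drafting caution applies. In the four-cell table, changing either connective from *or* to *and* removes the overlap and leaves no gap. If *elevations* is read as excluding normal values, that change alone leaves gaps: with *and* in Branch 1, a patient with one marker raised within its limit and the other normal meets neither branch; with *and* in Branch 2, a patient with one marker above its limit and the other normal meets neither. Stating the conditions in terms of values, with normal included, avoids this.

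The cost is one line in the table, plus the IRB review that Section 16.2 requires for a protocol change. Sample size, analysis, visits and data collection are unchanged.
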